## 5.5.7 T-cell Subsets and NK-cells

The following cell populations will be measured by flow cytometry analysis: Inflammatory Monocytes & Dendritic Cells, Recent Thymic Emigrants, CD4+, CD8+ Naïve & Memory Cells, CD4+ T Regulatory Cells, NK Cells,  $\gamma\delta$  T Cells, and B cells. These cells will be obtained from blood samples drawn at Days 0, 2, 4, 6 (just prior to and 4 hours after each T-Guard infusion) and at Days 14, 28, 56, and 180. The level of each population will be summarized using descriptive statistics at each assessment time considered. Changes in levels from baseline will be evaluated using Wilcoxon signed rank tests.

# 5.5.8 GVHD-related Biomarkers

Using the biomarker risk model from (Major-Monfried, Renteria et al. 2018), the serum levels of REG3 $\alpha$  and ST2, and the 3-IS urine levels at enrollment and Day 7, 14, and 28 post-initiation of T-Guard will be used to estimate NRM probabilities for each patient at Day 180 following each assessment time point. The proportions of patients with high risk (defined as an estimated NRM greater than 0.29) will be described at each assessment time.

Moreover, the proportions of patients experiencing a Day 28 CR will be described separately for patients with high risk vs. not using sample proportions and 95% Wilson score or Clopper-Pearson Cls, as appropriate.

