patients with severe hypoalbuminemia, with an albumin of less than or equal to 1 g/dl, a creatine kinase (CK) level greater than 5 times the upper limit of normal; patients with an uncontrolled infection (infections are considered controlled if appropriate therapy has been instituted and, at the time of enrollment, no signs of progression are present). Patients with evidence of relapsed, progressing, or persistent malignancy, or with evidence of minimal residual disease requiring withdrawal of systemic immune suppression are not eligible for this trial. Patients with known hypersensitivity to any of the components murine monoclonoal antibodies (mAb), or Recombinant Ricin Toxin A-chain (RTA), or have received more than one allo-HSCT, or who have known human immunodeficiency virus infection are also excluded from this trial. Pregnant or breastfeeding females, and females of childbearing potential unwilling to use effective birth control from start of treatment until 30 days after the last infusion of T-Guard are not eligible to participate. Male patients who are sexually active and unwilling to use effective birth control from start of treatment until 65 days after the last infusion of T-Guard are not eligible.

- Interim Analysis: This trial will include one interim analysis for futility after 21 patients become evaluable for the primary endpoint. There will be no interim analyses for efficacy.
- Treatment Description:Patients will receive 4 doses of T-Guard treatment,
administered intravenously as four 4-hour infusions at least two
calendar days apart. Each dose consists of 4 mg/m² Body
Surface Area (BSA).

Accrual Objective: The target accrual is 47 patients initiating T-Guard treatment.

Accrual Period: Approximately 1 year is expected for accrual.

Study Duration:Patients will be followed for 180 days for a total study duration
of approximately 1.5 years.

Safety Monitoring:The rates of overall mortality and CTCAE Grade 4 or higher
capillary leak syndrome (CLS) at Day 30 post treatment
initiation will be monitored separately using sequential
probability ratio tests (SPRT) for binary data. The SPRTs will
contrast a mortality rate of 15% vs. a 30% rate and a Grade 4
or higher CLS rate of 5% vs. a 15% rate.

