determined for similar RTA-based immunotoxins typically lies between 4 and 8 mg/m^2 with capillary leakage being the most common dose limiting toxicity (Amlot, Stone et al. 1993, Stone, Sausville et al. 1996, Engert, Diehl et al. 1997, Messmann, Vitetta et al. 2000, Schnell, Staak et al. 2002, Schindler, Gajavelli et al. 2011). Thus, given concern for increased toxicity due to the immunotoxin at higher doses, the Food and Drug Administration was in agreement with the proposed dose selection. In conclusion, the observed positive benefit-risk profile of the proposed dose regimen is considered sufficient to focus on confirming the safety and efficacy of T-Guard's current 4 x 4 mg/m^2 dose in a pivotal Phase 3 clinical study. In the proposed pivotal Phase 3 study, further data will be collected to investigate if biomarkers can be identified that correlate with clinical efficacy and safety.

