# 3.5.1.7 GVHD-related biomarkers

Serum ST2 and Regenerating Family Member 3 Alpha (REG3α) concentrations and urine 3-Indoxyl Sulfate (3-IS) concentrations at baseline and at Day 7, 14, and 28 post-initiation of T-Guard treatment will be used to estimate the probability of NRM at Day 180 post-assessment for each patient, using the NRM risk model from (Major-Monfried, Renteria et al. 2018). The proportion of patients with high risk biomarker status (defined as estimated NRM greater than 0.29) will be described at each time point.

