# Table 5-1: Observed and Adjusted Day 28 CR Rates from Meta-analysis of Phase I/II Study, MAGIC Controls, and REACH1 Study

The primary hypothesis will be evaluated by comparing the proportion of patients attaining a Day 28 CR to a historical rate of 30%, targeting 80% power to see a CR rate of 50% under T-Guard treatment. In addition, one interim analysis for futility will be incorporated. To generate the required sample size and futility and efficacy boundaries for this test, we used a Simon's two-stage minimax design. A sample size of 47 patients is required under this design to compare a null rate of 30% to an alternative rate of 50% with a one-sided type I error rate of 2.5% and 80% power.

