# 5.2 INTERIM ANALYSIS AND STOPPING GUIDELINES

## 5.2.1 Interim Analysis for Futility

This trial will include one interim analysis for futility. At the interim analysis, the number of Day 28 CRs will be compared to a futility boundary determined by Simon's two-stage minimax design comparing a null rate of 30% to an alternative rate of 50% with a one-sided type I error rate of 2.5% and 80% power. This is a non-binding stopping rule, in that the type I error rate will be controlled at 2.5% even if the rule is not followed exactly. If the number of CRs fails to exceed the boundary, the DSMB will be consulted on the appropriate course of action, including whether to declare futility and close the trial early.

The futility boundaries and operating characteristics of this design are displayed in Table 5- 2A. The interim analysis will be conducted when 21 patients are evaluable for Day 28 CR. If the number of CRs is 6 or below, the boundary is crossed. At the final analysis, the futility boundary is 20 CRs and efficacy is declared only if the observed number of CRs exceeds this boundary, i.e. the observed rate is at least 21/47 (44.6%).

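### Section 5.5.8 reduces the continuous GVHD biomarker risk to above or not above 0.29, discarding information that a few exploratory summaries of data already collected would keep

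*Combined protocol and SAP*

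**What the plan says.** The endpoint definition in Section 3.5.1.7 and the analysis in Section 5.5.8 agree. Serum ST2 and REG3α and urine 3-IS, measured at baseline (called enrollment in 5.5.8) and Days 7, 14 and 28, feed a cited risk model. The model gives each patient an estimated probability of NRM 180 days after each assessment.

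What is reported from it is a dichotomy. Section 3.5.1.7: "The proportion of patients with high risk biomarker status (defined as estimated NRM greater than 0.29) will be described at each time point". Section 5.5.8: "The proportions of patients with high risk (defined as an estimated NRM greater than 0.29) will be described at each assessment time". Section 5.5.8 adds one link to response: the proportion with Day 28 CR in high-risk and other patients, with 95% confidence intervals. It does not say which assessment time defines the two groups.

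No section plans a summary of the three analytes or of the estimated probability, a comparison with baseline, or a model of CR on the score. Three other repeated measures are handled differently. Anti-drug antibodies (5.4.13), cell subsets (5.5.7) and patient-reported outcomes (5.5.9) are described on their own scale, with change from baseline assessed by Wilcoxon signed rank test.

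The background in Section 1.3.3 says that "further data will be collected to investigate if biomarkers can be identified that correlate with clinical efficacy and safety".

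**The concern.** The continuous probability has to be calculated before the cut can be applied, so dropping it saves nothing and loses detail. A patient whose estimated NRM falls from 0.60 to 0.32 is counted as unchanged, while one who moves from 0.30 to 0.28 is counted as having left the high-risk group. For the link with CR, all patients above 0.29 are treated as alike, and so are all those at or below it.

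At stake is the precision of an exploratory result in a small trial: "The target accrual is 47 patients initiating T-Guard treatment". If the study is meant to show how the markers behave and whether they track response, the plan uses the least informative version of the data.

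**Working it through.** **The plan's own figure.** The only sample-size calculation is for Day 28 CR, 30% against 50%, "with a one-sided type I error rate of 2.5% and 80% power". An exact binomial calculation with boundaries 6/21 and 20/47 gives type I error 0.0227 and power 0.8001. The probability of stopping at the interim is 0.5505 at a 30% rate and 0.0392 at 50%. These match Table 5-2A (55.1% and 3.9%), and no smaller N from 40 to 46 meets both limits. Nothing comparable is stated for the biomarkers.

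**Inputs from the documents.**
- N = 47 treated (synopsis, 5.1).
- Day 28 CR expected at 50% (5.1.5).
- High-risk share 11/20 = 55% in the Phase I/II study (1.3.2.3), so 0.55 × 47 ≈ 26 high risk and 21 not.
- Expected Day 30 mortality 15% (5.2.2), so 0.85 × 47 ≈ 40 patients alive for a Day 28 sample.

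**Assumptions not in the documents.** A score that is normal on a transformed scale; the 55% share applying to the 0.29 cut here; log-odds of CR linear in the score; the odds ratios, correlations and shifts shown below; two-sided 5% tests.

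**Information kept by the cut.** For a normal score with high-risk share h and cut c, the efficiency relative to the continuous score is φ(c)² / [h(1 − h)]. With h = 0.55, c = −0.126 and φ(c) = 0.396, so 0.1567 / 0.2475 = 0.633. Then 47 × 0.633 ≈ 30 patients' worth of information. At h = 0.30 the efficiency is 0.576 (about 27 patients), and at h = 0.20 it is 0.490 (about 23).

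**Precision of the planned CR comparison.** With 26 and 21 patients and CR of 40% and 60%, the half-width of the 95% interval for the difference is 1.96 × √(0.4×0.6/26 + 0.6×0.4/21) = 0.28. At 30% and 70% it is 0.26.

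**Link with Day 28 CR, n = 47** (simulation; likelihood-ratio test on the continuous score against an uncorrected chi-square on the two groups):

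| Odds ratio per SD | Continuous | Cut |
|---|---|---|
| 1.5 | 27% | 18% |
| 2.0 | 62% | 43% |
| 2.5 | 82% | 62% |

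**Change from baseline, n = 40, fall of 0.4 SD** (simulation; Wilcoxon signed rank against mid-p McNemar, chosen because both then have size close to 5%):

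| Correlation | Continuous | Cut |
|---|---|---|
| 0.5 | 67% | 38% |
| 0.7 | 88% | 47% |

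Over falls of 0.3 to 0.5 SD the gain is about 21 to 41 points. Repeat runs move individual figures by a point or two.

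**The case against.** Much of the opposing case stands.

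- **The endpoint is exploratory and descriptive.** Section 5.1 calls the analysis descriptive, and 5.5.8 plans no biomarker test and no power target. The tests behind the power figures are illustrations. They measure how informative the two scales are, not the failure of a planned test.
- **The cut is legitimate.** It is fixed in advance and given alongside a cited risk model, so it is not data-driven. The high-risk proportion is a reasonable thing to describe.
- **The 55% share is borrowed.** It comes from a two-biomarker algorithm whose cut-off is not stated, whereas 5.5.8 lists three inputs.
- **The stated aim is general.** Section 1.3.3 is background and names no analyte. Section 3.5.1.6 attaches the search for a response marker to flow cytometry, which is analysed on its full scale. Nor is every continuous measure tested for change: corticosteroid dose (5.5.1) is only described.
- **More tests have a price.** Three analytes plus the score at three times would be 12 unadjusted tests, on survivors only, in a single arm where change cannot be attributed to treatment.

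A reader might infer that a real signal is likely to be missed because of the cut. The figures do not support that. At an odds ratio of 2.5 per SD the two-group version detects it 62% of the time, and at 1.5 both versions usually miss it. Small N is the main limit.

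A reader might also set the signed rank test against exact McNemar and obtain gains of 26 to 52 points. Part of that is unequal test size, because the exact test's true size here is only about 2 to 3%.

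What none of this answers is the omission itself: no section reports the continuous score or the analyte levels.

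**Conclusion.** The point holds as a modest one. Sections 3.5.1.7 and 5.5.8 discard information on change over time and on the link with Day 28 CR by reporting only which side of 0.29 a patient falls on. If the score is roughly normal and about 55% of patients lie above the cut, some 37% of the information is lost. The illustrative cost is about 9 to 20 points of power for the CR link and about 21 to 41 points for change. The direction does not depend on the assumed effect sizes in the settings examined, but the amounts do, and the documents give neither a distribution nor an effect size for the score.

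It would be wrong to read this as a threat to the trial's conclusion. N = 47, the 6/21 and 20/47 boundaries and the primary analysis do not depend on the biomarkers.

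The unstated time point for the CR comparison should be settled at the same time, since Day 28 risk status is concurrent with the response it would be compared with.

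**What to change.** In Section 5.5.8, with a matching line in 3.5.1.7:

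1. Keep the proportion above 0.29 at each time as a description.
2. Summarise ST2, REG3α and 3-IS (log scale) and the estimated NRM probability (logit scale) at each time.
3. Evaluate change from baseline in the estimated NRM score at Days 7, 14 and 28 by Wilcoxon signed rank test, as 5.5.7 does for cell subsets. Label it exploratory and restrict it to patients alive and sampled. Limiting this to the score keeps it to three tests.
4. Relate the baseline continuous score to Day 28 CR by logistic regression, reporting the odds ratio per SD with its 95% confidence interval, beside the two-group CR proportions.
5. State that baseline status defines the two groups in the CR comparison.

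The cost is SAP wording, a few extra tables and a small number of unadjusted exploratory tests. No new samples or patients are needed.

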#### 5.5.9 Patient-reported Outcomes

Patient self-reported measures will be assessed using selected PROMIS subscales for GI symptoms, physical function and satisfaction with participation in social roles. These instruments will be scored according to the recommendations of the developers. Scores at baseline and at Day 28, 56, and 180 will be described using descriptive statistics. Wilcoxon signed rank tests will be used to evaluate changes from baseline to each post-enrollment time point.

## **APPENDIX A: HUMAN SUBJECTS**

#### 1. Subject Consent

Candidates for the study will be identified as described in Chapter 4 of the protocol. The Prinicipal Investigator or his/her designee at each transplant center will contact the candidates, provide the patient with information about the purpose of the study, and obtain consent. The BMT CTN will provide a template of the consent form to each center. Each center will customize the templates according to their local requirements and submit for review by the DCC for adequacy prior to submitting to the NMDP IRB of Record. Each center must provide evidence of IRB approval to the DCC.

#### 2. Confidentiality

Confidentiality will be maintained by individual names being masked and assigned a patient identifier code. The code relaying the patient's identity with the ID code will be kept separately at the center. The ID code will be generated by and kept on file at the BMT CTN Data and Coordinating Center upon enrollment.

#### 3. Participation of Children, Women and Minorities

Women, ethnic minorities, children at least 12 and less 18 years of age, and other populations will be included in this study. Children less than 12 years of age are not eligible for this study given lack of applicable safety and PK data with T-Guard. Accrual of women and minorities at each center will be monitored to determine whether their rates of enrollment are reflective of the distribution of potentially eligible women and minorities expected from data reported to the CIBMTR and from published data on incidence of high risk acute GVHD in these groups. Centers will be notified if their rates differ significantly from those expected and asked to develop appropriate recruitment reports.

# APPENDIX B: LABORATORY PROCEDURES

**Collection of Mandatory Research Samples for Protocol-Defined Correlative Studies** Research samples will be collected for patients who consent to the BMT CTN 1802 study. Required research samples for study-specific exploratory endpoints include the collection of peripheral blood and urine samples as summarized in the table below. The following planned studies will be performed and remaining biospecimens made available to approved investigators for meritorious ancillary correlative laboratory studies with the potential to extend the findings of the current study portfolio.

- Analysis of serum cytokines before and after T-Guard infusions
- Evaluation of serum and urine biomarkers associated with acute GVHD
- PK of T-Guard development of a population pharmacokinetic model
- Evaluation of potential humoral responses (ADA) to T-Guard infusions
- Evaluation of T-Guard treatment on targeted and non-target immune cell subsets and presence of alloreactive and CMV/EBV specific T-cells

Once the samples are collected at specified time points they will either be shipped on the day of collection directly to specified project laboratory for testing or to the BMT CTN Biorepository for processing/long-term aliquot storage. In some cases, the samples will be transferred internally to a laboratory for local processing and freezing and then periodically batch shipped to the BMT CTN Biorepository for long-term storage and distribution for planned and approved studies. The collection and shipment of these blood and urine samples will be tracked using the network's GlobalTrace sample management system. Detailed procedures regarding specimen collection schedules, sample handling/processing procedures and shipping instructions will be found in the BMT CTN 1802 Research Sample Information Guide.

Subjects	Sample Type	Sample Collection Time Points	Sample Collection and Sample Processing Summary	Shipping Specifications	Shipping and Testing Locations
Patients	Peripheral Blood (SST Clot Tube) 5 mL Humoral Response Serum Anti-Drug Antibodies	Pre-treatment initiation Day -3 to Day 0 Post-treatment initiation Days 7, 14, 28, 90 and 180	Collect the blood sample and place 5 mL in SST Vacutainer tube containing no anticoagulant. Allow blood samples to clot upright for 30-60 minutes in a tube rack prior to centrifugation. Once centrifuged, the tube will be packaged for same- day shipping to Biorepository. Refer to the BMT CTN 1802 Research Specimen Information Guide for details related to sample centrifugation and shipping.	Centrifuged blood sample tube will be shipped at 2-8°C on the day of collection, to the BMT CTN Biorepository by priority overnight FedEx® delivery.	BMT CTN Biorepository
Patients	Peripheral Blood  (SST Clot Tube) 5 mL Serum Pharmacokinetic Testing	Day 0 (1 st T-Guard infusion) Prior to study drug infusion and 4, 5, 6, 8, and 24 hours after start of infusion Days 2 & 4 (2 nd & 3rd infusions) Prior to study drug infusion and 4, 6, and 24 hours after start of infusion Day 6 (4th infusion) Prior to study drug infusion and	Collect the blood sample and place 5 mL in SST Vacutainer tube containing no anticoagulant. Allow blood samples to clot upright for 30-60 minutes in a tube rack prior to centrifugation, serum removal and serum aliquot storage at -80°C. Refer to the BMT CTN 1802 Research Specimen Information Guide for details related to sample processing, aliquot labeling, storing and shipping.	Frozen serum sample aliquots will be periodically batched-shipped to the BMT CTN Biorepository by priority overnight FedEx® delivery.	BMT CTN Biorepository

	4, 6, 24, and 48 hours after start of infusion		

# **Required Research Sample Summary**

Subjects	Sample Type	Sample Collection Time Points	Sample Collection and Sample Processing Summary	Shipping Specifications	Shipping and Testing Locations
Patients	Peripheral Blood (SST Clot Tube) 10 mL Serum Cytokines and GVHD Biomarkers	Pre-treatment initiation Day -3 to Day 0 Post-treatment initiation Days 7, 14 and 28	Collect the blood sample and place 5 mL in SST Vacutainer tube containing no anticoagulant. Allow blood samples to clot upright for 30-60 minutes in a tube rack prior to centrifugation. Once centrifuged, the tube will be packaged for same- day shipping to Biorepository. Refer to the BMT CTN 1802 Research Specimen Information Guide for details related to sample centrifugation and shipping.	Centrifuged blood sample tube will be shipped at 2- 8°C on the day of collection, to the BMT CTN Biorepository by priority overnight FedEx® delivery.	BMT CTN Biorepository
Patients	Peripheral Blood (Sodium Heparin Vacutainer Tubes)	Pre-treatment initiation		Blood sample tubes will be shipped at 2- 8°C on the day of collection, to the	BMT CTN Biorepository

30 mL Peripheral blood mononuclear cells (PBMC)	Day -3 to Day 0 Post-treatment initiation Days 28 and 180	Collect the blood sample and place 10 mL into each of three Vacutainer tubes containing sodium heparin anticoagulant. Gently mix sample by inversion 8-10 times to mix sample well with anticoagulant.	BMT CTN Biorepository by priority overnight FedEx® delivery.	
CMV/EBV and Alloreactive T- Cells				

Subjects	Sample Type	Sample Collection Time Points	Sample Collection and Sample Processing Summary	Shipping Specifications	Shipping and Testing Locations
Patients	Urine (sterile transport tube) 10 mL GVHD Related Biomarkers	Pre-treatment initiation Day -3 to Day 0 Post-treatment initiation Days 7, 14, and 28	Collect 10 mL urine and place in sterile transport tube for same-day shipping to Biorepository. Refer to the BMT CTN 1802 Research Specimen Information Guide for details related to sample centrifugation and shipping.	Urine sample tube will be shipped at 2- 8°C on the day of collection, to the BMT CTN Biorepository by priority overnight FedEx® delivery.	BMT CTN Biorepository
Patients	Peripheral Blood  (Cyto-Chex BCT) 10 mL Immunophenotypi ng	Pre-treatment initiation Day -3 to Day 0 Day 0, 2, 4 and 6 1 st through 4 th T-Guard infusion Prior to study drug infusion and 4 hours after infusion Post-treatment initiation Days 14, 28, 56, and 180	Collect the blood sample and place 5 mL into each of two Cyto-Chex tubes containing EDTA anticoagulant and cell fixative. Gently mix sample by inversion 8-10 times to mix sample well with anticoagulant and cell fixative reagent.	Cyto-Chex blood tubes will be shipped at 2-8°C on the day of collection to the RPCI project laboratory by priority overnight FedEx® delivery.	Project Laborator y (RPCI)

Pharmcokinetic blood samples directly pre-infusion, and at 4, 5, 6, 8, and 24 hours after start of 1st infusion, pre-infusion, and at 4, 6, and 24 hours after the 2nd and 3rd infusion, and pre-infusion, and at 4, 6, 24 and 48 hours after the 4th T-Guard infusion. Pre-infusion samples should be drawn prior to T-Guard administration. A window of +/- 15 minutes for samples drawn at 4, 5, or 6 hours after the start of infusion, and a window of +/-30 minutes for the sample drawn 8 hours after the start of infusion is allowed. A window of +/- 2 hours for samples drawn 24 or 48 hours after the start of infusion is also allowed. Every effort should be made to collect PK samples at all timepoints, however, the treatment schedule should not be altered to accommodate PK sampling. For example, if T-Guard administration is scheduled for a weekend and PK sampling is not possible then administration should occur on schedule. In the event weekend PK sample collection is missed, collected pre-infusion and at 4 hours after the start of each infusion.  Peripheral blood for immunophenotyping should be collected pre-infusion and at 4 hours after the start of each infusion. Pre- infusion samples should be drawn prior to T-Guard administration and a window of +/- 15 minutes is allowed for the sample drawn 4 hours after the start of infusion.

